Study Design: 
This is a prospective, single-arm, multi-center post-market observational study assessing the performance of the Pipeline™ Flex Embolization Device with Shield Technology™ in subjects undergoing treatment for intracranial aneurysms in a large real-world, post-market setting.
	
Objective: 
To assess the performance of the Pipeline™ Flex Embolization Device with Shield Technology™ in subjects undergoing treatment for intracranial aneurysms in a large real-world, post-market setting.
	
Number of Subjects: Up to 200 subjects	Number of Study Centers: Up to 25 study centers
Duration of Study Participation: 
 • Enrollment Duration: Approximately 2 years • Follow-up: 1 Year • Total Study Duration: Approximately 3 years 	
Inclusion Criteria: 
 • Subject has provided written DRF or informed consent using the IRB/EC-approved consent form and agrees to comply with protocol requirements. • At least 18 years of age. • Subject has already been selected for flow diversion therapy as the appropriate treatment. • Subject has a target IA that has a parent vessel with diameter 1.5-5.0 mm distal/proximal to the target IA. 	

PROTOCOL SYNOPSIS

Sponsor: Medtronic Neurovascular

[name]

[name]

[contact]

Protocol Number: NV-PED-10

Product: Pipeline™ Flex Embolization Device with Shield Technology™

Regulatory Class: III

Exclusion Criteria:

1. Major surgery including endovascular procedures within the past 30 days.
2. Subject with target IA located in the basilar artery.
3. Subject with anatomy not appropriate for endovascular treatment due to severe intracranial vessel tortuosity or stenosis determined from baseline or pre-procedure imaging, or a history of intracranial vasospasm not responsive to medical therapy.
4. Stent is in place in the parent artery at the target IA location.
5. Subject with an acutely (within 30 days) ruptured aneurysm with a Hunt and Hess grade of 4 or higher.
6. Any known contraindication to treatment with the Pipeline™ Flex Embolization Device with Shield Technology™ per Instructions for Use.
7. The investigator determines that the health of the subject or the validity of the study outcomes (e.g., high risk of neurologic events, conditions that may increase the chance of stroke, worsening of clinical condition in the last 30 days) may be compromised by the subject's enrollment.
8. Pregnant or breast-feeding women or women who wish to become pregnant during the length of study participation.
9. Subject is currently enrolled or planning to participate in a potentially confounding drug or device trial during the course of this study. Co-enrollment in concurrent trials is only allowed when documented pre-approval is obtained from Medtronic.
10. Legal incapacity or evidence that a subject cannot understand the purpose and risks of the study or inability to comply fully with study procedures.

Treatment/Follow-up:

Eligible subjects will be treated with the Pipeline™ Flex Embolization Device with Shield Technology™.

Subjects will undergo standard of care follow-up visits. Data generated per standard of care will be collected for 1 year beyond the index procedure. All follow-up visits and telephone calls during this time period will be recorded. A summary of the data to be collected is listed in the table below.

In order to track compliance with antiplatelet therapy, subjects will be contacted at a minimum of approximately 1 (± 14 days), 3 (± 30 days), 6 (± 6 weeks), and 12 (± 8 weeks) months post-index procedure and asked to confirm their current antiplatelet regimen and that all relevant adverse events have been reported.

A survey will be administered to all centers to collect their standard antiplatelet therapy regimen at the start of the study and annually.

Time Period	Data to be Collected
Baseline	
• Relevant medical history and demographics• Aneurysm characteristics, symptoms and status (ruptured or unruptured)• Hunt & Hess Grade and WFNS (if ruptured)• Antiplatelet medication use within past 30 days• Other relevant concomitant medications• Platelet reactivity testing• NIH Stroke Scale (NIHSS)• Modified Rankin Scale (mRS)
Procedure	
• Relevant medications including antiplatelet regimen• Adverse events• Platelet reactivity testing• Procedure and fluoroscopy times• Study device information including side branches covered• Concomitant treatments• Deployment success at target IA• Imaging to be sent to the Core Lab*• Aneurysm occlusion• NIHSS• mRS
Post-Implant Follow-up	
• Relevant medications including antiplatelet regimen• Adverse events• Platelet reactivity testing• Imaging to be sent to the Core Lab*• Aneurysm occlusion• Retreatment• NIHSS• mRS

*All imaging taken (e.g., angiograms, CT, MR, rotational angiography with 3D reconstruction, cone-beam CT, etc.) should be provided to the Core Lab.

Statistical Analysis:

Descriptive statistics will be used to present the data and to summarize the study results. For continuous variables, statistics will include means, standard deviations, medians and ranges, as appropriate. Categorical variables will be summarized in frequency distributions. The unit of analysis for baseline demographics, study device usage and safety-related endpoints will be the subject. The unit of analysis for the device-related outcome will be the device. The unit of analysis for occlusion will be the aneurysm.

REVISION HISTORY

Revision	Effective Date	Change summary
Revision A	October 07, 2015	Initial Version
Revision B	June 24, 2016	
 • Australian requirements previously included in the addendum to Rev.A have been included in Rev.B. In particular: 
 - List of device models has been added in section 2.1.1 - The sentence "No other device or concomitant medications different from clinical practice have to be used during the SHIELD Study, since this is a post-market non-interventional study." has been added in section 5.4 - The sentence "Each investigator is to follow any individual local Competent Authority, Ethics Committee, IRB and TGA safety reporting requirements." has been added in section 6.2 - The sentences "It is the responsibility of the investigator and the clinical study teams to report all product complaint(s) associated with a medical device distributed by Medtronic, regardless whether they are related to intended use, misuse or abuse." and "All Regional Reporting requirements shall be followed: details will be specified in the Safety Management Plan." have been added in section 7. - The sentence "The regional Sponsor Medtronic Australasia is a wholly owned subsidiary of Medtronic Inc., which as the parent company of such entity maintains appropriate clinical study liability insurance coverage as required under applicable laws and regulations and will comply with applicable law and custom concerning specific insurance coverage. If required, a Clinical Trial Insurance statement/certificate will be provided to the EC/IRB." has been added in section 13.1 - The sentence "For Australia, the Investigator shall retain and preserve a copy of all Study Materials, including copies of signed consent forms, Case Report Forms, Clinical Investigation Plan, information relating to the Investigational Product, correspondence and investigator files for at least 15 years from Study Completion and must ensure that no Study related materials are destroyed before the expiration of this time period without the written approval of Sponsor. The Institution agrees to notify the Sponsor before destroying any Study Materials and agrees to retain the Study Materials for such longer period as reasonably required by the Sponsor at the Sponsor's expense." has been added in section 14.2 - Appendix A – Investigators list & Study Staff has been added

		
 • The development phase has been removed from the synopsis; • The number of patients has been changed in 200 (protocol synopsis and sections 4.1 and 4.2); • The number of sites has been changed in up to 25 (protocol synopsis and section 4.2); • The enrollment duration and the total study duration have been changed in approximately 2 years and approximately 3 years respectively (protocol synopsis and section 4.1); • Suggested FU windows have been added in the protocol synopsis and in sections 5.5 • The maximum number of patient enrolled for site has been changed in 30 in section 4.2; • Visit windows have been removed from sections 3.1 and 9.4; • The first sentence in section 5.12 has been changed from "The Sponsor may choose to discontinue the study should the Sponsor discover additional information during the study that may cause harm to subject safety." to "The Sponsor may choose to discontinue the study if the Sponsor discovers additional information during the study that may cause harm to subject or negatively affect subject safety." • The adverse events causality assessment has been changed following the new regulations in section 6.1; • The list of adverse events that can be adjudicate by the CEC in section 8.1 has been removed since all events of interest will be adjudicate; • The characterization of major strokes has been added in section 9.4; • EC and IRB have been added as authorities that can request to have access to patient medical files in section 11.1; • Previous section 11.2 "Monitoring report" has been removed; • Experience Statement from Principal Investigators and Sub-Investigators has been added in section 17.4; • The possibility to conduct ORACLE training also through a website has been added in section 17.5; • The definition of stroke has been modified in section 21 while the following definitions have been added: Neurological Death, Transient Ischemic Attack (TIA), cerebral infarction, Intra-Cranial Hemorrhage (ICH).
--	--	---

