4 STUDY DESIGN

This is a prospective, single-arm, multi-center post-market observational study to assess the performance of the Pipeline™ Flex Embolization Device with Shield Technology™ in subjects undergoing treatment for intracranial aneurysms.

4.1 Expected Duration of the Study and Subject Participation.

Up to 200 subjects who meet the Inclusion/Exclusion Criteria may be enrolled over a period of approximately 2 years to reach a target number of subjects. Study participation includes initial screening and baseline evaluation, treatment using the Pipeline™ Flex Embolization Device with Shield Technology™, and follow-up visits at the discretion of the treating physician for 1 year beyond the index procedure. The total study duration is expected to be approximately 3 years.

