5.9.3 Lost to Follow-up

A subject will be considered lost to follow-up if the subject cannot be reached after three (3) attempts to contact the subject for a follow-up visit. The site must document a minimum of three (3) attempts, and the final documented attempt should be made via registered letter.

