times as many subjects, the small sites will be ranked by size and divided into 2 pooled assignments using an alternating sequence (ABABAB). If the pooled smaller sites represent a site that has more than three times as many subjects as the largest single site, however less than 4 times as many subjects, the small sites will be ranked by size and divided into 3 pooled assignments using an alternating sequence (ABCABCABC).

Imputation of Outcome Data

Missing data for subjects who fail to complete study follow-up without any evidence of a major stroke in the territory supplied by the treated artery or neurological death will be imputed in the analysis of primary safety using the multiple imputation procedure from SAS (Proc MI). Subjects who withdraw from the study prior to completion and have experienced a major stroke in the territory supplied by the treated artery or neurological death at any time will be counted as having experienced the event of interest. A separate tabulation will be provided based on the observed data: subjects who withdraw from the study prior to completion without any evidence of a major stroke in the territory supplied by the treated artery or neurological death will be counted as not having experienced the event of interest. For effectiveness, since follow-up imaging of the target aneurysm was not required at each study visit but was instead performed according to standard of care, the primary endpoint will be assessed using a selection rule, according to the following preferences:

- Imaging from day 141 (the opening of the 6-month follow-up window) onward is eligible to be included; imaging earlier than day 141 is disregarded for this analysis but imaging after the end of the 1 year window is still eligible.
- We will use the last adjudicated image at any time starting from day 141, UNLESS
- - o The last image is a CTA and there is a DSA within 90 days prior to the CTA, in which case the DSA will be used, OR
 - o The last image is an MRA and there is a DSA or CTA within 90 days prior to the MRA, in which case the DSA or CTA will be used. For this sub-rule we will prefer DSA over CTA if both exist.

The rules above define the available data for the purpose of endpoint calculations and effectiveness tables and listings. For subjects with no qualifying imaging per the above preference rules, multiple imputation will be employed to handle missing data for primary effectiveness.

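### Protocol 5.9.3 declares a subject lost without a proxy, records or vital-status check, so an endpoint event unknown to the site is imputed or counted as no event in primary safety

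*Protocol*

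**What the plan says.** - **Visits.** Protocol 4.1 provides for "follow-up visits at the discretion of the treating physician for 1 year beyond the index procedure". The schedule in SAP Section 5 marks follow-up as required at 1, 3 and 6 months and 1 year, but NIHSS, mRS and imaging at those times are optional.
- **Fixed contact.** The synopsis (Treatment/Follow-up) and Protocol 5.5 set a minimum of four contacts with the subject, in order to track antiplatelet compliance. At each the subject is "asked to confirm their current antiplatelet regimen and that all relevant adverse events have been reported". Section 5.5 ties the relevant events to Section 6.
- **Loss to follow-up.** Under Protocol 5.9.3 a subject is lost who "cannot be reached after three (3) attempts to contact the subject for a follow-up visit". At least three attempts must be documented, and "the final documented attempt should be made via registered letter". No other enquiry is required.
- **Primary safety analysis.** SAP 7.4 applies multiple imputation to "Missing data for subjects who fail to complete study follow-up without any evidence of a major stroke in the territory supplied by the treated artery", and handles the neurological-death component the same way. A separate observed-data tabulation counts subjects who withdraw with no evidence of an event as non-events. A subject who withdraws after a known event is counted as an event.
- **Sensitivity analyses.** SAP 7.9 lists a worst-case analysis and a tipping-point analysis for primary effectiveness. It lists neither for primary safety.

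**The concern.** Death or severe disability can itself be the reason a subject does not answer. If the event happened at another hospital and nobody told the site, the loss rule asks for no step that would uncover it. The endpoint then causes its own missing value.

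Imputation that borrows from subjects who stayed in contact cannot recover such an event. SAP 7.4 names no covariates and no departure from missing at random. The observed tabulation goes further in the same direction, because it scores the subject as event-free.

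What is at stake is the 1-year rate of major stroke in the treated territory or neurological death, the primary safety endpoint. SAP Sections 3 and 6 intend to set the results beside Pipeline studies without Shield Technology, and Section 3 mentions a US indication evaluation. In that comparison a shift of one or two points would count.

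**Working it through.** The plan states no loss rate, power or precision figure, so there is none to reproduce. The background rates in Protocol 1.2.3 do reproduce: 6/107 = 5.6% (PUFs), 13/191 = 6.8% and 12/191 = 6.3% (ASPIRe).

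**Inputs from the documents.** N = 200 attempted deployments (SAP Section 5). Rate in those followed 5.6%, with 6.8% as an alternative (Protocol 1.2.3). Threshold 15% and exact two-sided 95% interval (SAP Section 6).

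**Assumptions, not in the documents.** L = 10, 20 or 30 subjects lost. A share q of the lost had an event unknown to the site. Imputation is represented by its expectation under missing at random, so it returns the rate in those followed.

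**Step 1: size of the bias.**
- True rate = (0.056 × (200 − L) + q × L) / 200
- Imputed rate ≈ 5.6%
- Observed tabulation = 0.056 × (200 − L) / 200

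| L | q | True rate | Imputed | Observed tabulation |
|---|---|---|---|---|
| 20 | 10% | (10.08 + 2)/200 = 6.0% | 5.6% | 10.08/200 = 5.0% |
| 20 | 20% | (10.08 + 4)/200 = 7.0% | 5.6% | 5.0% |
| 20 | 30% | (10.08 + 6)/200 = 8.0% | 5.6% | 5.0% |
| 10 | 20% | (10.64 + 2)/200 = 6.3% | 5.6% | 10.64/200 = 5.3% |
| 30 | 20% | (9.52 + 6)/200 = 7.8% | 5.6% | 9.52/200 = 4.8% |

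With 20 lost, the imputed rate is low by 0.4 to 2.4 points. Each unseen event is worth 1/200 = 0.5 point in the true rate.

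**Step 2: reading against 15%.** The SAP gives no decision rule, so I take an upper limit below 15% as the favourable reading. With N = 200 the Clopper-Pearson upper limit is 14.4% at 19 events and 15.02% at 20. The unseen events needed are 20 minus the events in those followed, in whole numbers:

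| Lost | At about 5.6% followed | At about 6.8% followed |
|---|---|---|
| 10 | 20 − 11 = 9 of 10 | 20 − 13 = 7 of 10 |
| 20 | 20 − 10 = 10 of 20 | 20 − 12 = 8 of 20 |
| 30 | 20 − 10 = 10 of 30 | 20 − 12 = 8 of 30 |

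The smallest share is 8/30 = 27% of the lost. With fewer lost, the share needed is larger.

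**The case against.** The strongest reply is that safety capture does not rest on the call. Adverse event status is evaluated throughout the study (Protocol Section 6). SAEs are due within 24 hours of the site learning of them, and death documents are requested (6.2). Sites commit to pursuing safety outcomes (17.2). All of this stands, but each provision presupposes that the site has heard of the event or goes looking for it. None is a required step before loss is declared.

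A reader might infer that subjects who die or have a disabling stroke become dropouts by rule. The documents do not support that. A known event counts even if the subject later withdraws, and imputation applies only where there is no evidence of one. Section 5.9.3 does not forbid a proxy or records enquiry, and a call or registered letter may itself reveal a death. Practice is simply left to each of up to 25 sites.

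A reader might also infer that the subject decides which events are relevant. Protocol 5.5 refers the term to Section 6, which lists neurological, device-related, procedure-related, bleeding and serious events.

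Timing narrows the exposure. In ASPIRe most major events fell within 30 days (12/191), and in PUFs the rate was 5.6% at 180 days and still 5.6% at five years. Early events would usually be known to the site, so the gap concerns mainly late events managed elsewhere. On that evidence the 20% and 30% scenarios, which need 4 and 6 unseen events among 20 lost, are pessimistic. One or two unseen events would move the true rate by 0.5 to 1.0 point. Late events are not negligible by design, however: the endpoint runs to 1 year, and intracerebral hemorrhage after 30 days is a secondary safety endpoint.

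Finally, the list of additional safety analyses in SAP Section 5 is blacked out, so a safety sensitivity analysis could stand there. The readable list in 7.9 has none.

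**Conclusion.** The point holds in a limited form. The loss rule requires no check beyond trying to reach the subject. An endpoint event unknown to the site is therefore imputed or scored as no event, and the readable SAP lists no analysis that would test primary safety for this. The direction of the possible bias is downward.

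Its size cannot be known from the documents. Under the assumed 20 lost and 10% to 30% affected, the imputed rate is low by about 0.4 to 2.4 points, and the observed tabulation by about 1 to 3 points (6.0 − 5.0 to 8.0 − 5.0). This matters for the comparison with earlier Pipeline rates. It would be wrong to infer that the reading against 15% is in doubt: that takes at least 27% of 30 lost subjects, or 40% to 50% of 20. The conclusion rests on the assumed loss rate, the assumed event share among the lost, and imputation under missing at random.

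**What to change.** 1. **Protocol 5.9.3.** Before a subject is declared lost, require a contact with next of kin or the family doctor, a hospital-records check and a vital-status check, where local law and the consent form or DRF allow. Events found this way go to the CEC and count as observed.
2. **SAP 7.9.** Add a worst-case and a tipping-point analysis for the primary safety endpoint, parallel to those for effectiveness.

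The first change costs consent or DRF wording for proxy contact, EC/IRB submission where applicable, and a small site effort for the few subjects who cannot be reached. It adds no visit or procedure. The second needs only programming. It remains possible even if much of the follow-up is already complete, as the past tense in parts of SAP Sections 5 and 7.4 suggests it may be.

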1 INTRODUCTION

1.1 Purpose

The primary study objective is to assess the performance of the Pipeline™ Flex Embolization Device with Shield Technology™ in a large real-world, post-market setting.

1.2 Background and Significance

1.2.1 Clinical Background

Intracranial aneurysms (IAs) are common cerebrovascular abnormalities with a prevalence of 0.5-6% in adults.¹⁻⁴ Most IAs are asymptomatic until they rupture, which can occur suddenly and without warning. Rupture of an IA may lead to cerebral bleeding or subarachnoid hemorrhage (SAH), a devastating complication with a case-fatality rate of 51%.^{5,6} Nearly half of SAH survivors are functionally incapacitated, with less than 5% having good outcomes.^{5,6} Aneurysm size influences the likelihood of rupture and correlates with morbidity and mortality. Compared to smaller aneurysms, large aneurysms have a 3-fold higher probability of rupture within 5 years of diagnosis while giant aneurysms have a 9-fold higher probability of rupture within 1-2 years.^{7,8} The ultimate goal of treatment of an unruptured aneurysm is to prevent rupture, while treatment of a ruptured aneurysm aims to prevent further hemorrhage.

1.2.2 Treatment

Despite advances in microsurgical techniques, treatment of large, giant, and wide-necked unruptured aneurysms with surgical clipping remains challenging and carries an associated mortality of 15-21% and morbidity of 9-35%.⁹ Occlusion rates can be high for surgical clipping, however, many aneurysms are not amenable to open surgery and the procedure carries considerably higher overall risk.¹⁰⁻¹² The rates of morbidity and mortality for coiling range between 2.3-13% and 1.3-6.7%, respectively.¹³⁻¹⁹ Coiling with balloons or stents has relatively low procedural risk, but these interventions have diminished efficacy for large, complex aneurysms, with occlusion rates as low as 40%.²⁰ Consequently, these low occlusion rates lead to high (27-50%) recurrence rates, may require retreatment, and ultimately place the patient at continuing risk for rupture.²⁰⁻²⁵ Flow diverters such as the Pipeline™ Embolization Device (PED) have created a paradigm shift in the endovascular treatment of unruptured IAs, and their safety and efficacy have been demonstrated consistently.²⁶⁻³⁶ Several studies evaluating the use of PED for treatment of unruptured small, large, and giant aneurysms have demonstrated achievement of high complete occlusion rates of 68-94.4% that are maintained up to 2-3 years after the index procedure with overall 0-13.9% associated morbidity/mortality rates.^{27,31,37} These rates compare very favorably to that reported in the literature with the use of conventional IA treatments of surgical clipping or coiling.^{25,38}

